## 9.2.7 Duration of new oxygen used

Duration of new oxygen used will be calculated and will be compared between the treatment arms using the negative binomial regression with time in ICU as the offset.

## 9.2.8 Number of patients receiving new mechanical ventilation

The number and percentage of participants who received new mechanical ventilation will be presented. Comparison between the treatment arms will be performed using a Fisher's Exact test.

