As patients requiring admission to hospital for treatment of COVID-19 are more likely to be older, there is likely to be a higher rate of co-morbid disease which may affect the patient's ability to consent, e.g. dementia. With a symptom of high temperature being a feature of COVID-19 there may also be a proportion of patients experiencing delirium which could affect their capacity to give informed consent. It is felt that it is important to include these patients in the trial to give a representative sample of patients with COVID-19, especially as older patients and those with underlying medical conditions are likely to have poorer outcomes. Where patients are thought to lack the capacity to give informed consent, this will be sought from their legal representative. The participant's treating clinician will make the decision as to whether the participant lacks capacity.

In Scotland those who can act as legal representative are:

- Personal legal representative i.e.
 - o Adult's Welfare Guardian or Welfare Attorney, or if not appointed:
 - o The adult's nearest relative, if neither are reasonably contactable:
- Professional legal representative, i.e. a doctor responsible for the medical treatment of the adult if they are independent of the trial, or a person nominated by the healthcare provider.

In England and Wales those who can act as a legal representative are:

- Personal legal representative, i.e. a person not connected with the conduct of the trial who is suitable to act as the legal representative by virtue of their relationship with the adult, and is available and willing to do so. If one is not available:
- Professional legal representative, i.e. a doctor responsible for the medical treatment of the adult if they are independent of the study, or a person nominated by the healthcare provider.

The PIS which the legal representative will receive will include:

- That they are being asked to give consent on behalf of the incapacitated adult,
- That they are free to decide whether they wish to make this decision or not,
- That they are being asked to consider what the adult would want, and to set aside their own personal views when making this decision,
- Sufficient information, in an understandable form, about the trial to ensure that they can make an informed decision.

The participant themselves will also receive information, according to their capacity of understanding, about the trial and its risks and benefits.

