#### Mechanical ventilation:

- 1. Ventilation free days
- 2. Incidence and duration of new mechanical ventilation use during the trial

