## 7.4 Missing Data

(ICH E3; 9.7.1, 11.4.2.2. ICH E9;5.3. EMA Guideline on Missing Data in Confirmatory Clinical Trials)

All reasonable efforts will be taken to minimise loss to follow-up, which is expected to be minimal as data collection for primary and secondary outcomes using trial-specific eCRFs is combined with linkage to routine clinical data on study outcomes. The number and percentage of participants with follow-up information at day 29 after the randomisation will be reported. For all participants who were discharged and alive but have missing clinical status, a clinical status scale of 2 (Not hospitalised, limitation on activities) will be applied.

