## 7.6 Preliminary analysis

An analysis for preliminary efficacy and safety will be performed on an unlocked database using the full analysis population. The preliminary analysis will focus on the primary endpoints and a limited number of key secondary endpoints plus safety. The endpoints to be evaluated in the preliminary analysis are as follows:

Primary endpoint: Clinical Status on the WHO ordinal scale at day 29

Key secondary endpoints: Time to improvement on the ordinal scale, proportion of patients requiring mechanical ventilation, mortality, duration of hospitalization

Safety: Proportion of patients with one or more adverse events, proportion of patients with serious adverse events

Virologic efficacy of Brensocatib: Neutrophil elastase measurement in blood by treatment arm.

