## 8 Summary of Study Data

All continuous variables will be summarised using the following descriptive statistics: n (non-missing sample size), mean, standard deviation, median, maximum and minimum or median for non-normally distributed data with their interquartile range. The frequency and percentages (based on the non-missing sample size) of observed levels will be reported for all categorical measures. All summary tables will be structured with a column for each treatment in the order (Control, Experimental) and will be annotated with the total population size relevant to that table/treatment, including any missing observations.

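### SAP 9.2.8 counts a death without ventilation as a non-event, so a shift from being ventilated to dying unventilated can read as benefit

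*SAP*

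**What the plan says.** SAP 4.2 lists the outcome as "Incidence and duration of new mechanical ventilation use during the trial", and Protocol 3.7 lists the same outcome. SAP 9.2.8 sets the analysis: "The number and percentage of participants who received new mechanical ventilation will be presented", followed by "Comparison between the treatment arms will be performed using a Fisher's Exact test". Neither section mentions death.

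Two general rules bear on it. SAP 8 fixes the denominator: "The frequency and percentages (based on the non-missing sample size) of observed levels will be reported for all categorical measures". SAP 7.4 has one imputation rule, which opens "For all participants who were discharged and alive but have missing clinical status, a clinical status scale of 2". It does not reach participants who died.

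SAP 7.6 gives the endpoint prominence in the preliminary analysis: "Key secondary endpoints: Time to improvement on the ordinal scale, proportion of patients requiring mechanical ventilation, mortality, duration of hospitalization".

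Death is dealt with elsewhere. It is the worst category of the primary scale (SAP 4.3), it has its own survival analysis (SAP 9.2.12), and hospital stay is restricted to those discharged alive (SAP 9.2.11).

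**The concern.** Death without ventilation rules out later ventilation, so it is a competing event. A participant who dies unventilated has a known answer to whether new ventilation was received, and the answer is no. Under the SAP 8 denominator rule that participant stays in the table as a non-event, beside those who recovered. The SAP does not say this in words; it follows from the definition and the denominator.

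The ventilation proportion can therefore fall for two opposite reasons: fewer patients deteriorate, or more of those who deteriorate die before or without ventilation. Fisher's test cannot tell them apart. Protocol 1 names avoiding the need for ventilation as a leading aim of treatment, so a favourable result here would be given weight. Unventilated deaths are plausible in this trial. Protocol 7.3 chooses to include patients who lack capacity and notes that "older patients and those with underlying medical conditions are likely to have poorer outcomes". That is an inference about who might die unventilated, since the passage says nothing about ventilation.

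**Working it through.** **Inputs from the documents.** 400 participants (SAP 5.1) randomised 1:1 (SAP 5.3) gives 200 per arm. The test is Fisher's exact (SAP 9.2.8). The type I error rate is 0.05 two-sided (Protocol 10.2).

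**The plan's own figure.** No figure is stated for the ventilation endpoint. The only figures to reproduce are those for the primary endpoint. Whitehead's formula is N = 12(z₀.₉₇₅ + z₀.₈₅)² / [ln(OR)² × (1 − Σp̄³)]. With OR 2 and the SAP Table 2 distribution this is 12 × (1.960 + 1.036)² / [0.4805 × 0.831] ≈ 270, against 272 stated. For OR 1.75 it gives 409.5 against 412. At N = 400 and OR 1.75, power is 84.2% against about 85% stated. The 200 per arm is therefore a sound base.

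**Inputs not in the documents.** The cumulative rates of new ventilation and of unventilated death are not given. All counts below are assumed.

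**Worked example, 200 per arm.**

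| | Placebo | Brensocatib | Fisher p |
|---|---|---|---|
| Newly ventilated | 20 (10.0%) | 8 (4.0%) | 0.029 |
| Died unventilated | 10 (5.0%) | 26 (13.0%) | 0.008 |
| Ventilated or died | 20 + 10 = 30 (15.0%) | 8 + 26 = 34 (17.0%) | 0.68 |

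The first row is what SAP 9.2.8 tests. It would be the same if the 26 had recovered. With 22 unventilated deaths instead of 26, the last row is 30 vs 30 (p = 1.00) and the first is unchanged.

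**Would the mortality result expose it?** That depends on the fatality c among the ventilated, assumed equal in the two arms. Total deaths are 10 + 20c vs 26 + 8c. At c = 0 this is 10 vs 26, a plain signal. At c = 0.5 it is 20 vs 30. At c = 1 it is 30 vs 34, the same counts as the composite (Fisher p = 0.68), and mortality would show little.

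**Range.** Hold ventilation-or-death equal in the two arms and move a share of brensocatib patients from ventilated to died unventilated. Summing over both binomial distributions gives the chance of a significant Fisher result favouring brensocatib:

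| Ventilated on placebo | No shift | 2 points | 4 points | 5 points |
|---|---|---|---|---|
| 10% | 1.7% | 7.5% | 25.2% | 40.6% |
| 15% | 1.8% | 6.3% | 18.0% | 27.6% |

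Tested on the composite instead, the chance stays between 1.8% and 1.9%.

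**Low rates.** SAP Table 2 has 2% dead (4 of 200) and 1% on mechanical ventilation or ECMO (2 of 200). If those were the cumulative rates, the largest possible shift is 2 vs 0 ventilated, p = 0.50; significance needs at least 6 vs 0. The 1% is status on one day, so cumulative use could be higher. At an assumed 3%, a 2-point shift (two thirds of the ventilated) gives a 16.9% chance.

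**The case against.** The strongest reply is that the plan never shows ventilation alone. SAP 7.6 names mortality next to it, output Table 9 puts both in one table, SAP 9.2.12 gives mortality its own hazard ratio, and the primary scale ranks death worst. The label of key secondary belongs to the preliminary analysis only, and SAP 7.8 sets no formal hierarchy that depends on this test. All of that stands and limits the harm. It does not remove it: none of these outputs separates deaths after ventilation from deaths without it, and the worked example shows that mortality may or may not reveal the shift.

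Three stronger readings are tempting and are not supported.

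- A reader might infer from 2% dead against 1% ventilated in the sample size table that unventilated deaths will outnumber ventilations. Both figures are states on a single day. Some of the 2% may have died after ventilation, and anyone ventilated and weaned is in neither figure.
- A reader might infer that any drug that raises unventilated deaths lowers the ventilation rate. That holds only where those who died would otherwise have been ventilated. If they would not have been, the ventilation count does not move.
- A reader might infer that the direction reverses readily. Take 12% vs 10% ventilated with 5% of unventilated placebo patients dying: the placebo composite is 0.12 + 0.88 × 0.05 = 16.4%. Reversal needs unventilated mortality on the drug above (0.164 − 0.10)/0.90 = 7.1%. At 6% the composite is 0.10 + 0.90 × 0.06 = 15.4% and still favours the drug.

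**Conclusion.** The gap is real and follows from the SAP text: the ventilation comparison is open to a competing-event bias that can favour the drug when there is no benefit. Its size cannot be fixed from the documents. It is negligible if ventilation and death are as rare as the sample size table. It matters if about 10% or more of placebo patients are ventilated and several percentage points move to unventilated death: a 4-point shift raises the chance of a spurious favourable result from 1.7% to 25.2% at 10% ventilated. These figures assume 200 per arm, full ascertainment, and that the patients who shift would otherwise have been ventilated. The primary analysis is not affected. The point is worth correcting because the endpoint is called key secondary in SAP 7.6 and the correction is cheap.

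**What to change.** In SAP 9.2.8 and 7.6:

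- Keep new mechanical ventilation as the outcome listed in Protocol 3.7. It should not be reduced to a descriptive row.
- Add a between-arm comparison of new invasive mechanical ventilation or death by day 29, and state that it is the comparison used for interpretation.
- Report death without ventilation by arm as a row beneath it, in output Table 9 and in the preliminary analysis.

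The ordinal scale already separates invasive ventilation or ECMO (category 6) from death (category 7), so this needs one derived variable and no new data. Make the change before any unblinded result is seen and record it in SAP 14. The cost is small: the composite includes deaths in which ventilation was not at issue, and it overlaps the mortality analysis. The component rows let a reader see both.

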#### 9.2.9 No of days free from ventilation

Number of days free from ventilation will be compared between the treatment arms using negative binomial regression with time in ICU as the offset.

#### 9.2.10 Duration of new ventilation used

Duration of new ventilation used will be calculated and will be compared between the treatment arms using negative binomial regression with time in ICU as the offset.

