3.7. Table of endpoints/outcomes

Objectives	Outcome Measures	Timepoint(s)
Primary Objective Participant clinical status (on a 7- point ordinal scale) In accordance with WHO recommendations the primary endpoint will be determined by a pilot trial of the first 100 participants.	 7-point ordinal scale: Not hospitalised, no limitations on activities Not hospitalised, limitation on activities; Hospitalised, not requiring supplemental oxygen; Hospitalised, requiring supplemental oxygen; Hospitalised, on non-invasive ventilation or high flow oxygen devices; Hospitalised, on invasive mechanical ventilation or ECMO (Extracorporeal membrane oxygenation) Death. 	Up to day 29
Secondary Objectives	Outcome Measures	Timepoint(s)
Evaluate the clinical efficacy of Brensocatib relative to standard care in adult patients hospitalised with COVID-19	Clinical Severity Time to an improvement of one category from admission using 7-point ordinal scale. Participant clinical status on 7-point ordinal scale Mean change in the 7-point ordinal scale	Daily whilst hospitalised Days 3, 5, 8, 11, 15 and 29. Baseline to days 3, 5, 8, 11, 15 and 29.
	National Early Warning Score (NEWS): Time to discharge or to a NEWS of ≤ 2 and maintained for 24 hours, whichever occurs first. Change from baseline Oxygenation:	Daily whilst hospitalised Days 8, 15, 29
	Oxygen free days Incidence and duration of new oxygen use during the trial	1-29 days 0-29 days
	Mechanical Ventilation: Ventilator free days	1-29 days

	Incidence and duration of new mechanical ventilation use during the trial.	1-29 days
	Hospitalisation:	
	Duration of hospitalisation (days).	Date of admission and discharge
	Mortality:	
	28-day mortality	Date of death
Evaluate the safety of the	Cumulative incidence of SAEs	1-29 days
intervention through 28 days of follow-up as compared to the control arm	Discontinuation or temporary suspension of treatment	1-29 days
	Changes in white cell count, haemoglobin, platelets, creatinine, total bilirubin, ALT, and AST over time (hospitalised participants only)	Days 0/1, 3, 5, 8, 11, 15, 29
	Adverse events of special interest- hyperkeratosis, infections and dental complications	1-29 days
	dental complications	
Exploratory Objectives	Outcome Measures	Timepoint(s)
Exploratory Objectives Evaluate the virologic efficacy of Brensocatib	·	Timepoint(s) Day 15 and day 29

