## 9.2.6 No of days free from oxygen

Number of days free from oxygen support will be compared between the treatment arms using the negative binomial regression with time in ICU as the offset. Number of days will be calculated as the number of days free from oxygen support reported on the 7-point ordinal scale eCRF.

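### The SAP does not say how deaths enter the oxygen-free-day, ventilation-free-day and support-duration comparisons, so a survival benefit is attenuated and can be masked

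*SAP*

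**What the plan says.** Four secondary outcomes are day counts compared between arms by negative binomial regression:

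- SAP 9.2.10: "Duration of new ventilation used will be calculated and will be compared between the treatment arms using negative binomial regression". The sentence goes on to specify ICU time as the offset.
- SAP 9.2.9: "Number of days free from ventilation will be compared between the treatment arms using negative binomial regression with time in ICU as the offset".
- SAP 9.2.7: "Duration of new oxygen used will be calculated and will be compared between the treatment arms using the negative binomial regression", again with the ICU-time offset.
- SAP 9.2.6 (oxygen-free days) uses the same model and offset. It alone says how the count is formed: "Number of days will be calculated as the number of days free from oxygen support reported on the 7-point ordinal scale eCRF".

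None of the four gives a rule for a participant who dies, and nothing elsewhere supplies one. Protocol 3.7 only names the outcomes, for example "Incidence and duration of new mechanical ventilation use during the trial", over days 1-29. SAP 4.3 describes the ordinal scale and NEWS but not these counts. SAP 7.4 assigns a value only to people known to have left hospital alive: "For all participants who were discharged and alive but have missing clinical status, a clinical status scale of 2".

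Death is dealt with elsewhere. It is category 7 of the primary scale (SAP 4.3) and has its own log-rank comparison (SAP 9.2.12). Deaths are left out of the hospital-stay calculation (SAP 9.2.11).

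**The concern.** Without a rule, an analyst who follows the text counts days as they occurred. A participant who dies after 3 days on a ventilator then has a shorter duration than a survivor weaned after 14 days. On free days, death lowers the total only by ending the count, so a later death can still outscore a survivor.

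Both documents expect the drug to reduce time on oxygen or a ventilator (Protocol 1, SAP 3.1), and these outcomes address that directly. If mortality differs between arms, the comparison mixes the effect on support time with the effect on survival, and the survival part counts in the wrong direction or too weakly.

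SAP 9.2.6 leaves a further choice open. A day scored 7 (death) is not a day on oxygen, and the text does not say whether it counts as free.

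**Working it through.** The plan gives no figure for these four outcomes. Its sample size concerns the primary scale and is unaffected.

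**Inputs (all assumptions, none in the documents).** The base case covers ventilated participants only:
- mortality 50% on placebo, 25% on drug, with no other drug effect
- 7 ventilator days before death, 14 in survivors
- 2 ICU days before ventilation in everyone, 4 after it in survivors
- a 28-day horizon

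Each arm mean is m × (value if died) + (1 − m) × (value if survived), where m is mortality. Ratios are drug to placebo.

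**Ventilation duration, base case**

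1. Raw days: placebo 0.5×7 + 0.5×14 = 10.5; drug 0.25×7 + 0.75×14 = 12.25. Ratio 1.17.
2. ICU days are 2+7 = 9 for deaths and 2+14+4 = 20 for survivors, giving means of 14.5 and 17.25. Ventilator days per ICU day: 10.5/14.5 = 0.724 and 12.25/17.25 = 0.710. Ratio 0.98.
3. Death set to 28 days, as a benchmark only: 0.5×28 + 0.5×14 = 21.0 and 0.25×28 + 0.75×14 = 17.5. Ratio 0.83. With 29 days, 17.75/21.5 is also 0.83.

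Negative binomial fits to 40,000 simulated patients per arm gave the same three values: 1.17, 0.98 and 0.83.

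**Range.** The grid has 81 scenarios, all with mortality 50% vs 25%: 0, 2 or 4 ICU days before ventilation; 3, 7 or 10 ventilator days before death; 10, 14 or 18 in survivors; 0, 2 or 4 ICU days after.

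| Duration measure | Ratio | Scenarios above 1 |
|---|---|---|
| Raw days | 1.00-1.36 | 72 of 81 |
| With ICU-time offset (SAP) | 0.92-1.09 | 33 of 81 |
| Death as worst value | 0.76-0.89 | 0 of 81 |

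The reversal depends on timing. With 14 days to death and 10 to weaning, outside this grid, the raw ratio is 0.92. With mortality 40% vs 30% and base-case times, the three ratios are 1.06, 0.99 and 0.93.

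A second illustration assumes 12% ventilated, ventilated mortality 50% vs 30%, 6 days to death and 14 to weaning. It gives raw means of 1.21 and 1.38 over all participants, ratio 1.14. Before truncation at the horizon this is (0.3×6 + 0.7×14)/(0.5×6 + 0.5×14) = 11.6/10 = 1.16, whatever share is ventilated.

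**Ventilation-free days, base case**

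| Counting rule | Placebo | Drug | Ratio |
|---|---|---|---|
| Days alive only (death keeps 2) | 8.0 | 11.0 | 1.38 |
| Days after death count as free (death keeps 21) | 17.5 | 15.75 | 0.90 |
| Death = 0 | 7.0 | 10.5 | 1.50 |

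Here a ratio above 1 favours the drug. Dividing by mean ICU days, the first ratio becomes (11/17.25)/(8/14.5) = 1.16 and the second (15.75/17.25)/(17.5/14.5) = 0.76. In the second illustration, where 5% of the unventilated also die, the gain is 0.25 days counting days alive and 0.34 with death scored 0. About a quarter is lost (0.09/0.34).

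**Single patients.** Someone who dies unventilated on day 20 scores 0 ventilator days and 19 free days. A survivor ventilated for 14 of 28 days scores 14 and 14. The death ranks better on both counts.

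**Oxygen duration.** Suppose oxygen is used throughout the ICU stay (9 days in deaths, 20 in survivors) and for 0-10 further ward days in survivors. The ratio is then 1.19-1.27 raw and 1.00-1.07 with the offset. Oxygen-free days were not calculated separately.

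**The case against.** The strongest objection is that the SAP does not analyse raw days. A reader might infer from 1.14-1.17 that a life-saving drug will look worse on ventilation duration. The documents do not support that: early death shortens ICU time as well, so the offset removes most of the reversal. It does not repair the outcome. A benefit that reads 0.83 with death as the worst value reads 0.98, and the direction is still wrong in 33 of 81 scenarios. The offset is also undefined (log of 0) for anyone never in ICU, which is a separate problem.

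A reader might also infer that free days reverse. If only days alive count, the direction is right and the effect is merely smaller. Reversal needs days after death to count as free, and even then deaths must come sooner than weaning would have.

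The illustrations suit the concern. The second one implies placebo mortality of 0.12×0.5 + 0.88×0.05 = 10.4%, against 2% in SAP Table 2. Few deaths would make the absolute distortion small, and with 0.12×200 = 24 ventilated per arm any ratio would be imprecise. Both also assume that the drug saves lives without changing the need for ventilation or its duration, which is not the mechanism the protocol proposes. All of this stands as a limit on size. It does not supply the missing rule.

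Finally, death is fully counted in the primary scale and the mortality analysis, new ventilation is tested separately (SAP 9.2.8), and SAP 7.8 promises cautious interpretation. That limits the consequence to these secondary outcomes.

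**Conclusion.** The concern holds in this form: four secondary comparisons have no rule for death, and the literal reading gives death a favourable duration and less than the worst free-day value. A survival benefit is attenuated, can be masked, and under some assumptions is reversed.

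For ventilation duration under the SAP's own model, the expected ratio for a drug that only saves ventilated patients is about 1.0 (0.92-1.09), against 0.83 in the base case with death as the worst value. For ventilation-free days the base-case ratio is 1.38, 0.90 or 1.50 depending on an unwritten counting rule. These figures rest on assumed mortality, ventilator days and ICU days. The absence of a rule does not.

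It would go too far to say that the plan will make an effective drug look harmful, or that the primary conclusion or sample size is at risk. The change should still be made, because the choice would otherwise fall to the analyst and the data needed are already collected.

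**What to change.** In SAP 9.2.6 and 9.2.9, define the outcomes as days alive and free of oxygen or ventilation to day 29, scored 0 for anyone who dies by day 29. Compare the arms with death as the worst value; a rank-based or proportional-odds comparison does this directly.

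In SAP 9.2.7 and 9.2.10, report durations descriptively by arm and vital status, without a between-arm test. Do not impute 28 days for deaths, because never-ventilated deaths would then receive the maximum new ventilation. In the second illustration, imputed deaths would supply 0.104×28 = 2.91 of the placebo mean of 3.73 days (78%), and never-ventilated deaths 0.044×28 = 1.23 (33%).

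Fix the wording before allocation is unblinded. The cost is a few sentences and a derivation rule. The downside is that the free-day outcomes then combine death with support time; mortality is still reported on its own in SAP 9.2.12.
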